suffer from frailty and sarcopenia, are able to consume novel gel and protein-based nutritional supplements without reducing their appetite. Preliminary data also showed that nutritional supplementation over a three-month period improved functional performance (Ispoglou et al., 2017, Butterworth et al., 2019) and body composition (Ispoglou et al., 2016) of older people. This approach, using a novel nutritional supplement, is potentially an ideal way to improve protein and energy intake in these patients. However, this approach has not been tested in patients with intestinal cancer. We do not currently know whether the nutritional supplement is acceptable to, and can be taken by, these patients as means to enhance protein and energy intakes. We therefore wish to investigate a group of elective preoperative cancer patients, a group of post-operative cancer patients, and a group of emergency patients. This latter group often present in a frail condition, and do not have the opportunity to improve their health before they undergo emergency surgery. In addition to measuring the acceptability of the supplement to patients, we plan to use non-invasive techniques (bioelectrical impedance, hand grip strength and a 'get up and go test") before and after a short-term supplementation period (4 weeks) to gather evidence of its efficacy

Aims and Objectives

The research team aim to investigate the feasibility and acceptability of novel nutritional supplementation in bowel/pancreatic cancer patients preoperatively and patients who have emergency bowel surgery or planned colorectal cancer surgery postoperatively.

The project will be conducted in two parts: part A and part B. In part A of the feasibility study the key research question the research team will aim to answer is:

"Does consumption of a nutritional gel (65 ml) before an 'ad libitum' breakfast (eat as much as someone can eat) negatively affect appetite and energy intake compared to a breakfast alone (control)?"

The key outcomes measured will be nutritional intakes, appetite and palatability perceptions at the breakfast.

In part B of the feasibility study the key research question the research team will aim to answer is:

"Can participants (who also completed part A) consume two supplements daily over a longer period of time without compromising their ability to eat food?"

The key outcomes measured will be habitual nutritional intakes and monitoring compliance to the supplementation regime.

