A secondary question for participants in part B will be:

"Can short-term supplementation improve body composition and aspects of physical fitness?"

The secondary outcomes measured will be fat mass and fat free mass as measured by bioelectrical impedance, handgrip strength test and a get-up and go test.

Design

A) Participant Recruitment

There are three main groups of participants who will be included in the study, who will be male and female patients over the age of 60, are:

- 1) Bowel (n=8) or pancreatic cancer patients (n=8) planned to undergo (elective) surgery. Part A and B will need to ideally be completed before surgery. These planned surgical patients, once they have completed part A of the feasibility study, will complete part B (i.e. they will be asked to take a nutritional supplement twice a day for 4 weeks and as preparation for their impending surgery).
- 2) Bowel cancer patients who have undergone elective surgery (n=8). Part A and B will be completed after surgery. After they complete Part A, these surgical patients will be asked to take part in part B of the study (i.e. take the supplements for 4 weeks) once they have a return of bowel function and have begun tolerating diet and fluids as assessed and documented by a surgeon during daily post-operative review.
- 3) Patients undergoing emergency surgery from a range of clinical conditions (n=8). Part A and B will be completed after surgery as these patients cannot be assessed pre-operatively due to the urgent requirement for surgery. After they complete Part A, these emergency surgical patients will be asked to take part in part B of the study (i.e. take the supplements for 4 weeks) once they have a return of bowel function and have begun tolerating diet and fluids as assessed and documented by a surgeon during daily post-operative review.

B) Methodology

The two parts of the feasibility study are as follows:

Part A of feasibility study (Palatability and Appetite Assessment)

The experimental trial will involve consumption of an ad libitum breakfast and consumption of a 65 g essential amino acid based nutritional prototype 10 minutes before the ad libitum breakfast (intervention) or no additional gel supplementation(control). All patients will complete a control and an intervention visit. The patients will complete an appetite assessment for intervention and control visits (2 separate visits) and a palatability assessment for the intervention visit.

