the intervention.

• Functional capacity at the start and end of the intervention.

Handgrip strength test

The preoperative group (group 1) and postoperative groups (2&3) will follow the feasibility study on

different pathways:

Project Proposal

IRAS ID: 280595

GROUP 1(Preoperative):

Patients will need to visit our laboratories at Leeds Beckett campus on three occasions in total (each

visit will last ~30-60 min). The preoperative group of patients will eat a breakfast meal only on one

visit (condition 1 - control) and then a breakfast meal alongside a gel supplement (condition 2 -

intervention) on a second visit. On each occasion the patients will complete an appetite assessment

and be asked to complete a palatability assessment when they take the gel during the intervention

visit The patients will all complete an intervention (condition 2) and non-intervention (condition 1)

at random - ensuring they complete both conditions.

The two visits for the two conditions (1&2) will take place a week apart after an overnight fast for

which they will be given pre-test instruction leaflet to describe the preparations for the visit.

Patients or carers will be asked to record all food and fluid consumed in the 24 h prior to the first

experimental trial and replicate this for the next trial. Patients will also be asked to avoid alcohol and

intensive physical activity during the same time period.

During the second visit to Leeds Beckett campus the patients will have body composition assessment

(measured by bioelectrical impedance) and functional capacity will be measured by assessment of

handgrip strength test and a 'get up and go' test. These physical assessments will be measured twice

during the study; at the start during the second Leeds Beckett campus visit (Day 1 of

supplementation) and at the end of the supplementation intervention (after 4 weeks). During the

second visit to Leeds Beckett campus the patients will be given the food diary with explanation

about completion and a 4-week supply of gels to be taken at home twice daily alongside their

breakfast and lunch therefore starting Part B of the study.

Part B will focus on compliance with daily nutritional gel supplementation during a breakfast and

lunch time meal for 4 weeks. The patients will be asked to complete a paper food diary for 3 days

during the third week. The patient will return to the laboratory after 4 weeks (for their third and

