final visit to Leeds Beckett campus) bringing their completed food diary and any spare gels on this

visit. They will repeat the physical assessments described above on this final return visit.

GROUP 2 & 3 (postoperative cancer patients and postoperative emergency patients):

Project Proposal IRAS ID: 280595

These two groups will complete Part A - palatability test and consume an ad libitum breakfast

following their surgery during their hospital stay. They will not complete a second breakfast meal

assessment. They will be assessed by a senior member of the surgical team who will decide if their

bowel function has returned sufficiently to begin eating and drinking before they commence in part

A.

These two groups will not be required to perform an overnight fast before the palatability test and

will only complete the palatability/appetite test once.

No physical health assessments will be undertaken by group 2&3.

They will then enter Part B of the study and be given gel supplementation at breakfast and lunch

each day whilst they are recovering in hospital. They will continue the supplementation at home for

a total of 4 weeks and will complete a 3 day food diary during week 3 of the study. When these

patients return for their postoperative outpatient review at 4 weeks following their procedures, the

food diaries and spare gels will be collected by the research team.

Compliance to the regime will be monitored by counting any gels that have not been consumed. The

food diaries will be collected in both groups and stored on site at St James's University Hospital. The

diaries will be transcribed onto an electronic document that will be stored securely on Leeds

Teaching Hospitals Trust servers in a password protected hard drive area. The paper diaries will be

destroyed via the confidential waste system as per NHS protocols for information governance.

Eligibility

The elective patients presenting with cancer, will be identified and selected at the multidisciplinary

meetings by the colorectal and pancreatic consultant surgical team. The patients to be included in

the study will all be over 60 years old and will be subject to the following inclusion criteria:

• Patient has capacity to understand the study and give informed consent

• Patient is capable of ingesting the oral supplement

A senior member of the surgical care team will approach the patient either after diagnosis has been

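### Group 1 visit order is described both as control then gel and as random; run as control first, the gel comparison in Part A cannot be separated from visit order

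*Protocol*

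**What the plan says.** Under Aims and Objectives, the Part A key question is whether the gel before an ad libitum breakfast would "negatively affect appetite and energy intake compared to a breakfast alone (control").

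The Group 1 (Preoperative) pathway describes how the two conditions are delivered:

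- Patients have breakfast only on one visit ("condition 1 - control) and then a breakfast meal alongside a gel supplement"), the latter on a second visit.
- Two sentences later, in the same paragraph, they complete both conditions "at random - ensuring they complete both conditions".
- On timing: "The two visits for the two conditions (1&2) will take place a week apart after an overnight fast for" which patients receive a preparation leaflet.
- The second campus visit is labelled the first day of supplementation. The label is repeated under Data Analysis, Part B.

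Participant Recruitment sets the size of Group 1: "Bowel (n=8) or pancreatic cancer patients (n=8) planned to undergo (elective) surgery", so 16 patients.

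The protocol disagrees with itself on who has a control breakfast. The general Part A description under Methodology says "All patients will complete a control and an intervention visit". The Group 2 & 3 pathway says of those patients "They will not complete a second breakfast meal" assessment, and that they "will only complete the palatability/appetite test once".

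**The concern.** The two sentences cannot both govern visit order. Staff who follow the first would give every Group 1 patient the control breakfast first. Staff who follow the second would vary the order between patients. This is a matter of study conduct, so an analysis plan cannot settle it once the visits have taken place.

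Order matters because the two visits may differ for reasons other than the gel. The first is the patient's first test meal in the laboratory, eaten alone, and the first use of the appetite scales. The second comes a week later in patients awaiting cancer surgery. If intake or appetite shifts between visits, a control-first design credits the whole shift to the gel, in whichever direction it runs.

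Under the Group 2 & 3 pathway those patients have one breakfast and no control. Group 1 then carries the whole gel-versus-control answer to the Part A key question.

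**Working it through.** The protocol states no figure for balance, power or the size of a visit effect, so there is none to reproduce. The check has two parts.

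**The wording set side by side.** The sequential sentence, the numbering of control as condition 1 and gel as condition 2, and the day-1 label on the second visit all fit control first. One sentence, on completing the conditions at random, says otherwise. That sentence guarantees only that each patient does both conditions; it gives no sequence ratio.

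**What each order does to the estimate.** Let *g* be the gel effect and *p* the shift from visit 1 to visit 2 (unknown), with no carry-over between visits. The gel-minus-control difference has expectation *g + p* in a control-first patient and *g − p* in a gel-first patient. With n1 control-first and n2 gel-first patients (n1 + n2 = 16), the plain mean paired difference has expectation

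*g + p × (n1 − n2)/16*.

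- Control first for all, 16:0: *g + p*. All of *p* is included, and with one sequence *g* and *p* cannot be estimated separately.
- Balanced, 8:8: *g*. The shift cancels.
- Any split with both sequences present, averaging the two sequence means: ½[(*g + p*) + (*g − p*)] = *g*.

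**Chance imbalance if order is random.** As a reference case only, take unrestricted 1:1 allocation of 16, Binomial(16, ½):

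- P(exactly 8:8) = 12870/65536 = 19.6%.
- P(10:6 or worse) = 45.4%; the plain mean carries at least 4/16 = 25% of *p*.
- P(11:5 or worse) = 13770/65536 = 21.0%; at least 6/16 = 37.5% of *p*.
- P(12:4 or worse) = 7.7%; at least 8/16 = 50% of *p*.

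Over repeated allocations the expected bias is zero, and its root mean square is *p*/√16 = 25% of *p*. Averaging over sequences removes the shift at a cost in variance, relative to 8:8, of (16/4)(1/n1 + 1/n2): 4(1/11 + 1/5) = 1.16 at 11:5, and 4(1/12 + 1/4) = 1.33 at 12:4.

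**Illustration of the control-first case.** Assume no gel effect and a visit shift of 0.25, 0.5 or 0.75 SD of the paired difference. A two-sided 5% paired t-test on 16 patients (15 df, noncentrality 4 × the shift in SD, so 1, 2 or 3) then rejects in 15.5%, 46.5% or 80.1% of trials. The shifts and the test are assumptions; the protocol gives neither.

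**The case against.** The strongest reply is that random order is what the protocol intends. The sequential sentence speaks of one visit and a second visit and may only be introducing the two conditions. The sentence on completing them at random is the one that directly addresses allocation. The day-1 label is not decisive either: gels and diary are handed over at the second visit, when Part A is complete in either order, so the label may simply mark the handover. This stands as a plausible reading, and under it there is no systematic bias. It does not remove the conflict. A gel-first patient would eat a no-gel control breakfast on the labelled first day of supplementation, and the text nowhere explains that.

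The protocol also limits differences between visits: overnight fast, replication of the previous day's intake, restrictions on alcohol and intensive activity, and eating alone. These make a large shift less likely but do not deal with familiarity or change over the week. The direction of any net shift is unknown, since such influences could oppose each other.

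A reader might infer more than the text supports:

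- *That simple randomisation is planned, and is itself a bias.* The protocol is silent on the method, and sequence generation may sit in a document not shown. Chance imbalance has zero expected bias, and the percentages above apply to an unadjusted mean that the protocol does not specify.
- *That sites could follow different orders.* Group 1 test breakfasts are described at one laboratory only.
- *That the false effect can be stated in energy units.* No visit effect is given. The bowl is replaced before it is emptied, so one bowl is not expected intake.
- *That the pilot's primary objective is undermined.* Gel palatability is rated at the gel visit and does not need the control contrast.

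**Conclusion.** The concern holds as a contradiction about visit order in the Group 1 pathway. If control first is run for all 16 patients, 100% of any visit-order effect enters the gel-minus-control difference and cannot be recovered. If order is random, there is only chance imbalance, which a balanced list prevents and a period term removes. The documents do not show which order staff would follow, so confounding is a risk created by the wording, not an established feature of the trial.

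The size of any visit effect is unknown, and the rejection rates above are illustrations over an assumed range. That Group 1 is the only source of the comparison rests on the Group 2 & 3 pathway; the general Part A sentence giving all patients both visits contradicts it and must be reconciled. In Group 1 the order matters whichever of those two statements is kept. What is at stake is the Part A key question on appetite and energy intake, not the palatability objective.

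**What to change.** Before Group 1 recruitment:

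- Replace the sequential sentence with a statement that visit order (control-gel or gel-control) is randomised from a list prepared in advance and balanced 8:8, preferably 4:4 within bowel and 4:4 within pancreatic patients.
- Record the order each patient actually follows.
- State that the gel-control difference is averaged over the two sequences, that is, adjusted for period.
- Reconcile the label of the second visit as the first day of supplementation with patients who have the gel breakfast first.
- Reconcile the general Part A sentence with the Group 2 & 3 pathway on who has a control visit.

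The cost is a few sentences of protocol text and a 16-line list. The change to Group 1 order adds no patients, visits or procedures. The 4:4 balance is good practice for a sample this small; removing the conflicting order is the necessary part.

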The outcomes we will be measuring in all three groups are nutritional intakes, appetite and palatability perceptions at the breakfast.

The gel is the intervention and is manufactured by Vitrition UK Ltd (Product specification QD27 V8.

2. 25. 04. 2017.) See below composition per 65 grams gel:

Energy = 113.65 kcal, Carbohydrates = 21.936 grams, Protein: 7.5 g and all in the form of essential

amino acids, Sugars = 13.36 grams, Fats = 0 grams, Salt = 0.026 grams, 500 iu of vitamin D3.

The ad libitum breakfast will have an energy density of 4.9 kJ/g and a macronutrient composition of

59% carbohydrate, 18% protein and 23% fat. Meal preparation will involve mixing of 54 g of porridge

oats (Oatso Simple Original, Quaker Oats) with 292 ml semi-skimmed milk. The mixture will then be

cooked in a microwave for two and a half minutes at 700 W. Patients will need to consume the

breakfast in isolation to avoid any social influence on food intake. A bowl of the breakfast meal will

be provided by one of the investigators or a trained nurse and patients will be instructed to eat until

'comfortably full', with no time limit set for eating. This bowl will be replaced before the participant

empties it. Food intake will be calculated as the weighted difference in food before and after eating.

Appetite perceptions (hunger, satisfaction, fullness and prospective food consumption) will be

measured using 100 mm visual analogue scales with descriptors anchored at each end. A composite

appetite score will be calculated as the mean value of the four appetite perceptions after inverting

the values for satisfaction and fullness. Palatability ratings (visual appeal, smell, taste, aftertaste and

pleasantness) will be obtained for the supplements and the ad libitum breakfast. A composite

palatability score will be calculated as the mean value of the palatability subscales.

Part B of Feasibility study (Supplementation regime compliance and body composition)

Following completion of Part A, patients will be given 56 gels (to cover 4 weeks of supplementation,

twice daily (one gel alongside breakfast and one alongside their lunch meal). The patients will also

be given a 1 x3 day food diary to complete at home in week 3 of the supplementation intervention.

Outcome measures include:

• Nutritional intakes in a food diary.

Monitoring compliance to the supplementation regime.

Body composition assessment (measured by bioelectrical impedance) at the start and end of

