All participants will be given as long as is necessary for them to decide to participate in the pilot study. The planned surgical patients have a timeframe attached to planned surgery which will dictate a decision window. However, the research team would like to complete 4 weeks nutritional intervention before surgery in order to assess the benefit of the supplement. The post-operative and emergency patients will begin nutritional supplementation 48 hours following surgery and will be allowed to decide whether they want to participate during their inpatient stay, usually approximately 7 days if there are no postoperative complications. Assessment of the ability to tolerate oral fluids and therefore begin nutritional supplementation will be recorded in the patient records.

Potential unpalatability and intolerance of the oral supplement may arise but initial studies have been completed for the prepared nutritional supplements. Initial data show that the oral

supplement has been well tolerated so far. The nutritional supplement has been discussed with the Medicines and Healthcare Regulatory Agency and is not regarded as a medicinal product; therefore, a clinical trial of an investigational medicinal product is not required.

It is not anticipated that there will be any serious adverse events during the pilot study but in the event of occurrence then then a safety report form will be completed by the chief investigator and sent to the Research Ethics Committee as per the standard operating procedure of the Health Research Authority.

Time Schedule

It is anticipated that this feasibility study will be conducted over a 4-5 week period and will form the basis of a pilot study that will influence a clinical trial at a later stage.

Reference List

 Acute effects of essential amino acid gel-based and whey protein supplements on appetite and energy intake in older women. *Appl Physiol Nutr Metab*, 44, 1141-1149.
- DODDS, R. & SAYER, A. A. J. C. M. 2016. Sarcopenia and frailty: new challenges for clinical practice. 16, 455.

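### The single unused-gel count is home-only in Group 1 but mixes ward and home use in Groups 2 and 3, and there it can shift with length of stay and start day whatever the adherence

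*Protocol*

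**What the plan says.** The Aims and Objectives section makes compliance with the supplementation regime a key Part B outcome. The relevant provisions are these:

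- **Supply, all groups** (Part B of Feasibility study): "Following completion of Part A, patients will be given 56 gels (to cover 4 weeks of supplementation", at two a day.
- **Group 1 pathway:** patients receive "a 4-week supply of gels to be taken at home twice daily alongside their" breakfast and lunch. Supplementation starts at the second campus visit, and leftovers come back at the third visit, 4 weeks later.
- **Group 2 & 3 pathway, ward phase:** "They will then enter Part B of the study and be given gel supplementation at breakfast and lunch" each day while recovering in hospital.
- **Group 2 & 3 pathway, home phase:** "They will continue the supplementation at home for" 4 weeks in total, ward and home together.
- **Collection, Groups 2 and 3:** when "patients return for their postoperative outpatient review at 4 weeks following their procedures, the" diaries and leftover gels are taken in by the research team.
- **Measure:** "Compliance to the regime will be monitored by counting any gels that have not been consumed".
- **Start and stay** (Ethical Considerations): postoperative and "emergency patients will begin nutritional supplementation 48 hours following surgery", and the inpatient stay is "usually approximately 7 days if there are no postoperative complications".

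No count at discharge is planned. The clinical items listed under Data Management do not include a discharge date or a first-gel date. The protocol does not say whether ward gels are drawn from the patient's 56 or from separate stock, or how ward intake is recorded.

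**The concern.** The same number describes different things in the two halves of the sample. In Group 1 (n=16) it reflects use at home over a full 4 weeks. In Groups 2 and 3 (8 + 8 = 16) it combines gels offered on the ward with gels taken at home, in proportions set by length of stay. The window also closes on a date fixed by the operation rather than by the first gel.

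Two patients with identical adherence can therefore produce different counts. Part B asks whether patients can take two gels a day over a longer period, and the study is meant to inform a later trial. If that trial is planned on this figure, its designers cannot tell how much of any shortfall, or of any good result, comes from the patient and how much from the setting and the calendar. No later analysis can separate the phases if the gels were not counted at discharge.

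**Working it through.** Days are counted from surgery (day 0). Let *s* be the day of the first gel, *d* the day of discharge and *w* = *d* − *s* the ward days on gel. The uptake rates below are assumptions, because the protocol gives none.

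**1. The protocol's own figure.** 2 gels × 7 days × 4 weeks = 56, which agrees.

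**2. Ward share of the 56.** Share = 2*w*/56.
- Start day 2, discharge day 7 (the protocol's figures): *w* = 5, so 10/56 = 17.9%.
- Start day 2, discharge day 14 (assumed longer stay): *w* = 12, so 24/56 = 42.9%.
- Group 1: 0%.

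**3. Ceiling set by the collection date.** With collection on day 28 after surgery, the most a patient can take is 2(28 − *s*).
- *s* = 2: 52/56 = 92.9%.
- *s* = 5: 46/56 = 82.1%.
- *s* = 7: 42/56 = 75.0%.

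These are perfect users with ward gels drawn from the 56. In Group 1, where the window runs from the first gel, the ceiling is 56/56. The later starts are relevant because the Group 2 & 3 pathway makes Part A, and hence Part B, wait for return of bowel function. I therefore treat 48 hours as the earliest start.

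**4. Source of ward gels.** Suppose ward gels come from separate stock, the full 28 days are available, and leftovers are counted against 56. A perfect user then shows 2(28 − *w*)/56:
- *w* = 5: 82.1%.
- *w* = 7: 75.0%.
- *w* = 14: 50.0%.

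On this reading a longer stay lowers the figure.

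**5. Ward gels from the 56, full 28 days.** Compliance = [*w* × ward uptake + (28 − *w*) × home uptake]/28.

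| Ward / home uptake (assumed) | *w* = 5 | *w* = 14 |
|---|---|---|
| 100% / 70% | 75.4% | 85.0% |
| 70% / 70% | 70.0% | 70.0% |
| 60% / 80% | 76.4% | 70.0% |

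A longer stay raises the count, leaves it unchanged or lowers it, depending on two rates that a single count does not reveal.

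**6. Stay and start day together** (ward gels from the 56, collection on day 28, uptake 100% on the ward and 70% at home, denominator 56). Count = [2(*d* − *s*) × 1.0 + 2(28 − *d*) × 0.7]/56.
- Start day 2, discharge day 7: (10 + 29.4)/56 = 70.4%.
- Start day 2, discharge day 14: (24 + 19.6)/56 = 77.9%.
- Start day 7, discharge day 14: (14 + 19.6)/56 = 60.0%.

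Adherence is the same in all three patients. The counts span 18 points, and the two patients discharged on day 14 lie on either side of the one discharged on day 7.

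**The case against.** A reader might infer something stronger: that ward-given gels inflate compliance and make patients with longer, more complicated stays look more compliant. With assumed uptake of 95% on the ward and 60% at home, a full 28 days, and equal numbers staying 7 and 14 days, the mean would be 71% against 60% at home. The documents do not support this as a finding. It needs ward uptake above home uptake, ward gels drawn from the 56, and 28 full days of dosing. The protocol states neither of the first two, and its collection date conflicts with the third. Lower uptake on the ward is quite possible in patients just after surgery, and the Background itself notes reduced appetite. Nor does the Background's remark that about half of patients can have complications supply the equal split: it concerns colorectal and pancreatic cancer resection, gives no length of stay, and does not cover the emergency patients in Group 3.

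It can also be said that ward days are part of the planned regime, that the groups are deliberately put on different pathways, that no between-group comparison of compliance is announced, and that denominators are often left to an analysis plan, which is not at hand here. All of this is fair. It means that the whole-regime figure is legitimate and need not give way to a home-only one. It does not answer the data-collection point. An analysis plan can choose a denominator, but it cannot recover a discharge count that was never made. Hospital records may supply dates, but no planned record supplies the number of gels taken before discharge.

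**Conclusion.** The point holds as a defect of measurement, not as a bias of known direction. The count is home-only in 16 patients and a ward-plus-home mix in 16. About 18% of the gels fall on the ward in an uncomplicated stay, assuming a start at 48 hours and discharge on day 7. If collection is on day 28 after surgery and leftovers are set against 56, full adherence in Groups 2 and 3 appears as at most 93%, and as 75% with a start on day 7. Length of stay can push the count either way, so neither the sign nor the size of any distortion can be determined from the protocol. Compliance is a key Part B outcome, but the primary objective, palatability, is not affected. This is a cheap improvement worth making before recruitment.

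**What to change.** In the Group 2 & 3 pathway:

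1. Record the date of the first Part B gel.
2. Count the gels remaining on the day of discharge and record that date.
3. State whether ward gels come out of the patient's 56, and how they are recorded if they do not.
4. Keep the overall figure and report inpatient and home compliance beside it, each as gels taken over gels due in that phase up to collection.
5. Reconcile the 4-week supplementation period with collection at 4 weeks after the procedure. The two statements do not fit together, and which of them should change is for the investigators to decide.

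The first and third patients in step 6 of the working show the effect. Both would have ward compliance of 100% (10/10 and 14/14) and home compliance of 70% (29.4/42 and 19.6/28), in place of single counts of 70.4% and 60.0%. A perfect user would show 100% in each phase.

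The cost is one extra count and two dates in 16 patients. The phase-specific figures will rest on fewer days, with as few as 10 ward gels per patient in an uncomplicated stay, and should be presented as descriptive.
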